5.2. General Methods

In general, number and percent will be presented for binary variables. Number, mean, standard deviation (or standard error of the mean), median, minimum, and maximum will be presented for continuous variables. In addition, graphics may be used to present the data.

5.2.1. Analyses for Binary Data

The normal approximation for the difference in binomial proportions will be used to assess the difference between active and placebo.

The normal-approximation to the test statistic for the difference in binomial random variables is calculated as

$$Z_i = \frac{\hat{p}_i - \hat{p}_c}{\sqrt{\frac{\hat{p}_i(1-\hat{p}_i)}{n_i} + \frac{\hat{p}_c(1-\hat{p}_c)}{n_c}}}$$

where \hat{p} refers to the relative frequency, n to sample size, the subscript c refers to the control group (eg, placebo) and the subscript i refers to the active group.

Two-sided 95% confidence intervals are formed by:

$$(\hat{p}_i - \hat{p}_c) \pm Z_{0.975} \sqrt{\frac{\hat{p}_i(1-\hat{p}_i)}{n_i} + \frac{\hat{p}_c(1-\hat{p}_c)}{n_c}}$$

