9.1. Sample Size Determination

The primary endpoint of the study will be the change from baseline in SDAI at 8 weeks. The study will enroll approximately 50 completers allocated as follows:

PF-06651600 (200 mg) (N)	Placebo (N)
30	20

Assuming a 15% dropout rate* the study will enroll approximately 60 subjects.

The study will have over 90% power to detect separation from placebo, assuming a 13 point difference in response between the placebo and 200 mg arm (standard deviation is assumed to be 14 points for both arms*) and controlling Type-I error rate at 5% level. More detailed sample size considerations will be discussed in the SAP.

**Based on information from Phase 3 tofacitinib studies.*

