5.3.1. Binary Endpoint

For the binary response endpoints (eg, SDAI remission rates), subjects with missing values will be handled by:

- non-responder imputation (NRI) method, ie, setting any missing values to be non-responsive (0)
- will be used as observed (ie, excluding any missing values from analysis)

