6.2. Secondary Endpoint(s)

6.2.1. SDAI

Analysis of number of subjects with SDAI remission (SDAI \leq 3.3) and SDAI low disease activity (SDAI \leq 11) at Weeks 4, 6, and 8:

- ITT population set
- Missing data imputation
 - Observed

- NRI
- Normal approximation

Analysis of change from baseline in SDAI at Weeks 1, 2, 4, 6, and 8:

- ITT population set
- Missing data imputation – none (Observed)
- MMRM

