6.2.2. DAS

For DAS28-3 (ESR), DAS28-3 (CRP), DAS28 -4 (ESR), and DAS28-4 (CRP), analysis of number of subjects with DAS28 remission (DAS<2.6) and DAS28 low disease activity (DAS28<3.2) at Weeks 4, 6, and 8:

- ITT population set
- Missing data imputation
 - Observed
 - NRI
- Normal approximation

Analysis of change from baseline in DAS28-3 (ESR), DAS28-3 (CRP), DAS28 -4 (ESR), and DAS28-4 (CRP)SDAI at Weeks 1, 2, 4, 6, and 8:

- ITT population set
- Missing data imputation – none (Observed)
- MMRM

6.2.3. hsCRP

Analysis of change from baseline in hsCRP at Weeks 1, 2, 4, 6, and 8:

- ITT population set
- Missing data imputation – none (Observed)
- MMRM

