9. APPENDICES

Appendix 1. SUMMARY OF EFFICACY ANALYSES

All efficacy analyses will be based on ITT set. Treatment groups will be PF-06651600 and placebo.

Primary Efficacy Endpoint	Statistical Method	Missing Data
Change from baseline in SDAI at Week 8	ANCOVA with baseline SDAI as a covariate	Observed
Change from baseline in SDAI at Week 8	ANCOVA with baseline SDAI as a covariate	LOCF
Change from baseline in SDAI at Week 8	ANCOVA with baseline SDAI and anti-TNF use as covariates	Observed
Change from baseline in SDAI at Week 8	ANCOVA with baseline SDAI and anti-TNF use as covariates	LOCF
Change from baseline in SDAI at Week 8	Bayesian analysis of posterior distributions of the SDAI scores and placebo adjusted change from baseline	-

Secondary Efficacy Endpoints	Statistical Method	Missing Data
SDAI remission and low disease activity at Weeks 4, 6, and 8	Normal approximation	Observed
SDAI remission and low disease activity at Weeks 4, 6, and 8	Normal approximation	NRI
DAS28-3 (ESR), DAS28-3 (CRP), DAS28 -4 (ESR), and DAS28-4 (CRP) remission and disease activity at Weeks 4, 6, and 8	Normal approximation	Observed
DAS28-3 (ESR), DAS28-3 (CRP), DAS28 -4 (ESR), and DAS28-4 (CRP) remission and disease activity at Weeks 4, 6, and 8	Normal approximation	NRI

Change from baseline in SDAI at Weeks 1, 2, 4, 6, and 8	MMRM	Observed
Change from baseline in DAS28 (eg, DAS28-3 (ESR), DAS28-3 (CRP), DAS28 -4 (ESR), and DAS28-4 (CRP)) at Weeks 1, 2, 4, 6, and 8	MMRM	Observed
Change from baseline in hsCRP at Weeks 1, 2, 4, 6, and 8	MMRM	Observed
Change from baseline in in the Tender/Painful and Swollen Joint Count (28) at Weeks 1, 2, 4, 6, and 8	MMRM	Observed
Change from baseline in PhGA of Arthritis at Weeks 1, 2, 4, 6, and 8	MMRM	Observed

Outcomes Research Endpoints	Statistical Method	Missing Data
-----------------------------	--------------------	--------------

Change from baseline in in PAAP VAS and PtGA of Arthritis VAS at Weeks 1, 2, 4, 6, and 8	MMRM	Observed
Change from baseline in in the HAQ-DI at Weeks 1, 2, 4, 6, and 8	MMRM	Observed

CCI

CCI

ACR20, ACR50, and ACR70 at Weeks 4, 6, and 8	CCI	
ACR20, ACR50, and ACR70 at Weeks 4, 6, and 8	CCI	

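### The unpooled Wald test and interval in SAP 5.2.1 are unreliable for remission and low-disease-activity rates at about 30 vs 20, and there is no rule for zero or near-zero placebo counts

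*SAP*

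**What the plan says.** SAP 5.2.1 gives one method for binary data: "The normal approximation for the difference in binomial proportions will be used to assess the difference between active and placebo". It introduces the statistic with "The normal-approximation to the test statistic for the difference in binomial random variables is calculated as" and the interval with "Two-sided 95% confidence intervals are formed by". Both displayed formulas use the unpooled variance, p(1-p)/n summed over the two arms, and the interval uses the 0.975 normal quantile.

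SAP 6.2.1 ("Analysis of number of subjects with SDAI remission" and low disease activity) and SAP 6.2.2 (the same two rates for four DAS28 versions) list the normal approximation and nothing else. Appendix 1 repeats this, for example for "SDAI remission and low disease activity at Weeks 4, 6, and 8". SAP 5.3.1 has each rate analysed twice, once as observed and once with missing values counted as non-response.

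That makes 2 × 3 × 2 = 12 SDAI comparisons and 4 × 2 × 3 × 2 = 48 DAS28 comparisons, 60 in all. Neither document offers an exact, score or continuity-corrected alternative, a minimum count, or a zero-cell rule. On arm sizes, Protocol 9.1 says: "The study will enroll approximately 50 completers allocated as follows", namely 30 active and 20 placebo.

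**The concern.** The Wald variance for an arm with no responders is exactly zero. A placebo result of 0/20 is then treated as a rate known without error, and all the uncertainty in the interval comes from the active arm. Placebo is also the smaller arm, so the understatement tends to favour active. A remission table could show an interval excluding zero when the data do not support that.

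If neither arm has a responder, the test statistic does not exist and the interval has zero width. That states certainty about no difference when there is almost no information, and it would force a choice of method after unblinding.

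Sparse counts are plausible for remission. The Protocol introduction says that conventional DMARDs seldom bring it about. Placebo patients stay on methotrexate after an inadequate response, and entry requires at least 6 tender and 6 swollen joints. SDAI remission requires a score of 3.3 or less, assessed as early as Week 4. Sparse counts are less clearly expected for low disease activity.

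**Working it through.** **Inputs.** Completers 30 vs 20 and 15% dropout (Protocol 9.1). The plan's enrolment figure reproduces: 50/0.85 = 58.8, stated as about 60. At the same 3:2 ratio, 60 randomized gives 36 vs 24. That split is inferred, not stated, and is used here as the size under non-responder imputation. No document gives an expected rate, so rates below are assumed ranges.

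**Formula (SAP 5.2.1).** d = p_A - p_P; SE = √[p_A(1-p_A)/n_A + p_P(1-p_P)/n_P]; Z = d/SE; interval d ± 1.96 SE.

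- 4/30 vs 0/20: SE = √(0.1333 × 0.8667/30 + 0) = 0.0621; Z = 0.1333/0.0621 = 2.15.
- 7/30 vs 1/20: SE = √(0.2333 × 0.7667/30 + 0.05 × 0.95/20) = 0.0913; Z = 0.1833/0.0913 = 2.01.
- 0/30 vs 0/20: SE = 0; Z = 0/0; interval [0, 0].

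**The same tables with other methods.**

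| Active vs placebo | Wald p | Wald 95% CI | Miettinen-Nurminen 95% CI | Fisher p |
|---|---|---|---|---|
| 0/30 vs 0/20 | undefined | 0 to 0 | -16.4% to 11.6% | 1 |
| 3/30 vs 0/20 | 0.068 | -0.7% to 20.7% | -7.1% to 25.8% | 0.27 |
| 4/30 vs 0/20 | 0.032 | 1.2% to 25.5% | -4.0% to 29.9% | 0.14 |
| 5/30 vs 0/20 | 0.014 | 3.3% to 30.0% | -0.8% to 33.7% | 0.075 |
| 6/30 vs 0/20 | 0.006 | 5.7% to 34.3% | 2.3% to 37.5% | 0.069 |
| 7/30 vs 1/20 | 0.045 | 0.4% to 36.2% | -3.3% to 37.3% | 0.12 |
| 4/36 vs 0/24 | 0.034 | 0.8% to 21.4% | -3.5% to 25.5% | 0.14 |

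Newcombe intervals agree with Miettinen-Nurminen on whether zero is excluded in each row. Barnard's p for 4/30 vs 0/20 is 0.11. Against 0/20, Wald excludes zero from 4/30 and the score intervals from 6/30. Against 1/20 the thresholds are 7/30 and 9/30; against 0/24 they are 4/36 and 6/36.

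**How often.** P(no placebo responders) = (1-p)^n. At true rates of 2%, 5% and 10% this is 67%, 36% and 12% for n = 20, and 62%, 29% and 8% for n = 24. Both arms empty at a common 3%: 0.97^50 = 22% (30/20) and 0.97^60 = 16% (36/24).

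**Type I error of the Wald test**, by enumerating every possible table under independent binomials with a common rate:

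| Common rate | 30/20 two-sided | 30/20 favouring active | 36/24 two-sided | 36/24 favouring active |
|---|---|---|---|---|
| 3% | 0.8% | 0.7% | 1.3% | 1.1% |
| 5% | 2.6% | 2.2% | 3.8% | 3.1% |
| 10% | 6.5% | 5.0% | 7.3% | 5.3% |
| 15% | 7.1% | 5.0% | 7.4% | 4.9% |
| 20% | 6.8% | 4.3% | 7.0% | 4.3% |

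The peak at 36/24 is 7.5%. For Miettinen-Nurminen at 30/20 the two-sided error is 3.3% at a 10% rate and 3.9% at 15%, with 1.0% and 1.6% favouring active.

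The link to zero cells can be seen directly. At a 10% rate and 30/20, the error favouring active from tables with no placebo responder is P(placebo = 0) × P(active ≥ 4) = 0.90^20 × 0.3526 = 0.1216 × 0.3526 = 4.3%, out of the 5.0% total.

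**The case against.** **No decision depends on these rates.** The SAP's decision rule (5.1) concerns only the Bayesian Week 8 SDAI analysis, no alpha or power is set for any binary endpoint, and counts will be printed beside the intervals. This is right and limits the weight of the point. It does not make the specified interval correct.

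**Few tables change.** The methods conflict only at 4 and 5 of 30 against 0/20, 7 and 8 of 30 against 1/20, and 4 and 5 of 36 against 0/24. A zero cell alone does no harm: 1 to 3 of 30 vs 0/20 gives p from 0.31 to 0.068. Fisher's later threshold (7/30 against 0/20) overstates the gap because Fisher is conservative here. All of this stands, but these are counts a small trial can produce.

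**At very low rates the test is conservative.** At common rates of 5% or less the two-sided error stays under 5%, and inflation appears only from about 8%. This also stands. It concerns error under equal rates, and does not rescue the intervals at 4/30 vs 0/20 or 0/30 vs 0/20.

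**The placebo rate is assumed.** True: the only pointer is qualitative, and for low disease activity the zero-cell case has no direct support in the documents.

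**A one-line sparse-cell rule would be enough.** It would cover zero cells, but 7/30 vs 1/20 shows that the conflict does not need one. A single method for all counts also avoids switching on observed data.

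**Conclusion.** The concern holds. SAP 5.2.1 specifies a method that fails outright when both arms have no responders. With zero or one placebo responder, it excludes zero at active counts about two responders lower than score intervals require. Two-sided error reaches about 7.1% (30/20) and 7.5% (36/24), and the share favouring active is about twice nominal at a 10% common rate. Coverage at common rates of 10% to 20% is 92.5% to 93.5%, against 95.1% to 96.8% for Miettinen-Nurminen.

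The assumptions are the inferred 36/24 split and the range of true rates. Denominators under imputation could be slightly smaller because the ITT set requires at least one dose; observed denominators at Weeks 4 and 6 could exceed 30/20. The table-by-table results at the sizes shown need no assumed rate. The effect is confined to secondary endpoints in a Phase 2a trial, so the plan should be changed, but the primary conclusion is not at risk.

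**What to change.** In SAP 5.2.1, replace the Wald Z and interval with the Miettinen-Nurminen score interval for all binary efficacy endpoints, under both observed and non-responder handling. Newcombe's interval is an acceptable alternative. If p-values are reported, use an unconditional exact test such as Barnard's; Fisher's test is valid but conservative at these sizes. State that the same method applies when one or both arms have no responders, and align the entries in SAP 6.2.1, 6.2.2 and Appendix 1. The ACR response rates, whose method is redacted, need the change only if they rely on 5.2.1.

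The cost is one SAP paragraph, matching labels and a standard procedure option. Data collection and the primary analysis do not change. The downside is somewhat wider intervals when counts are sparse.

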9.4. Randomization

The indicator of prior exposure and inadequate response to anti-TNF α treatment will be used as a stratification variable for randomization. Randomization will be stratified to achieve equal proportion of anti-TNF α inadequate responders in all arms.

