5.2.2. Analyses for Continuous Data

Mixed Effect Model Repeat Measurement (MMRM) for Longitudinal Continuous Data:

The fixed effects of treatment, visit, and treatment-by-visit interaction will be included, along with patient as a random effect. Unstructured covariance matrix will be assumed.

When modeling the change from baseline values, the variable of visit will start with the first post-baseline visit, and the actual baseline value will be included as a covariate. At each visit, estimates of mean values and the mean differences between the active treated group and the placebo group will be derived from the model. The corresponding p-values, standard errors and 95% confidence intervals will also be derived from the model.

Below is an example of potential statistical analysis system (SAS) code:

```
PROC MIXED DATA=XXX;
  CLASS SUBJID TREATMENT VISIT;
  MODEL CHGBASE=TREATMENT VISIT TREATMENT*VISIT BASE/ALPHA=0.05 DDFM=KR;
  REPEATED VISIT/SUBJECT=SUBJID TYPE=UN;
  LSMEANS TREATMENT*VISIT/ALPHA=0.05 CL DIFF;
RUN;
```

Analysis of Covariance (ANCOVA) for Non-longitudinal Continuous Data:

The non-longitudinal continuous data will be analyzed by ANCOVA with treatment as the factor. When modelling change from baseline values, the actual baseline value will be included as a covariate. Active dose group will be contrasted versus placebo.

Below is an example of potential SAS code:

```
PROC MIXED DATA=XXX;
  CLASS TREATMENT;
  MODEL CHGBASE=TREATMENT BASE/ALPHA=0.05;
  LSMEANS TREATMENT/ALPHA=0.05 CL PDIFF;
RUN;
```

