6.5. Subset Analyses

Summary statistics for the SDAI endpoints will be presented by baseline smoking status and by previous anti-TNF use.

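### The SDAI and DAS28 low-disease-activity and remission comparisons ignore the baseline score, at the cost of a modest loss of precision and some sensitivity to chance baseline imbalance

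*SAP*

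**What the plan says.** SAP 5.2.1 is the only method section for binary data: "The normal approximation for the difference in binomial proportions will be used to assess the difference between active and placebo". Its Z statistic and 95% interval use the two observed proportions and the arm sizes, with no covariate.

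The method is applied as follows:
- SAP 6.2.1: "Analysis of number of subjects with SDAI remission" (SDAI <=3.3) and low disease activity (SDAI <=11) at Weeks 4, 6 and 8.
- SAP 6.2.2, for each of four DAS28 versions: "DAS28 remission (DAS<2.6) and DAS28 low disease activity (DAS28<3.2) at Weeks 4, 6, and 8".
- SAP Appendix 1: the rows for "SDAI remission and low disease activity at Weeks 4, 6, and 8" and their DAS28 counterparts list the normal approximation alone, once with observed data and once with non-responder imputation (NRI).

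For change-from-baseline models, SAP 5.2.2 states that "the actual baseline value will be included as a covariate", and the primary Bayesian model in SAP Appendix 4 has a baseline SDAI term.

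Two other provisions touch on baseline, but neither covers the baseline score. Protocol 9.4: "The indicator of prior exposure and inadequate response to anti-TNF α treatment will be used as a stratification variable for randomization". SAP 6.5: "Summary statistics for the SDAI endpoints will be presented by baseline smoking status and by previous anti-TNF use".

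**The concern.** A fixed cut-off asks for a different improvement from each patient. To reach SDAI <=11, someone starting at 30 must improve by 19 points and someone starting at 50 by 39. Protocol 4.1 sets lower limits for entry (at least 6 tender and 6 swollen joints, hsCRP of at least 7 mg/L) but no upper limit on SDAI, so starting scores can differ widely. Randomisation does not balance the score by design.

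With 30 against 20 completers, the arms can differ by several SDAI points by chance. The continuous analyses allow for that and the state endpoints do not. If the arms prove uneven, the responder difference will partly reflect where patients began, and a choice to adjust made after unblinding would be hard to defend. A prognostic covariate that is already collected also goes unused.

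**Working it through.** **Scope.** SDAI has 2 states and the four DAS28 versions have 4 x 2 = 8. That makes 10 states at 3 visits, or 30 comparisons, each run as observed and with NRI.

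**The plan's own figure.** Protocol 9.1 gives difference 13, SD 14, 30 vs 20 completers, 5% error and power over 90%. The standard error is 14 x sqrt(1/30 + 1/20) = 4.04, and 13/4.04 = 3.22. Power is 94.2% one-sided; two-sided it is 89.6% (normal) or 88.3% (t). The figure reproduces to within about 2 points. Neither document states power or precision for the binary endpoints.

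**Inputs for the check**
- From the documents: SD of change 14 and difference 13 (Protocol 9.1); placebo improvement 13.7 (prior mean, SAP Appendix 4); 30 vs 20.
- Assumed, because the documents do not give them: baseline mean m = 38-42, baseline SD s = 10-14, slope b of improvement on baseline = 0.2-0.6. Steeper slopes were also tried.

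**Model.** Improvement = 13.7 + 13A + b(x - m) + error, with total within-arm SD 14 (A = 1 on active, x = baseline). Then:
- Week 8 mean = m - 13.7 - 13A
- Week 8 SD: T = sqrt[((1-b)s)^2 + 14^2 - (bs)^2]
- Response rate = Phi(z), with z = (11 - mean)/T

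**Dependence on the starting score** (m = 40, s = 12, b = 0.5). Residual SD = sqrt(196 - 36) = 12.65. On active, from baseline 30, expected improvement is 26.7 - 5 = 21.7 against 19 needed: Phi(0.21) = 58%. From baseline 50 it is 31.7 against 39 needed: Phi(-0.58) = 28%.

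**Worked case** (m = 40, s = 12, b = 0.3)
1. T = sqrt(70.56 + 183.04) = 15.92.
2. Active: mean 13.3, z = -0.144, rate 0.443. Placebo: mean 26.3, z = -0.961, rate 0.168. Difference about 0.275.
3. Crude standard error = sqrt(0.443 x 0.557/30 + 0.168 x 0.832/20) = 0.123.
4. SD of the chance baseline difference = 12 x sqrt(1/30 + 1/20) = 3.46 points.
5. Each arm's rate falls by phi(z)(1-b)/T per baseline point: 0.0174 active, 0.0111 placebo. A between-arm difference D splits on average as 0.4D (active) and -0.6D (placebo). The shift is therefore D x (0.4 x 0.0174 + 0.6 x 0.0111) = 0.0136D.
6. At 1 SD (D = 3.46) the shift is 0.047, or 0.38 of a standard error. At D = 5 it is 0.068; simulation also gave 0.068, and -0.001 after adjustment.
7. Share of variance removable = (0.047/0.123)^2 = 14.6%. The simulated crude-to-adjusted variance ratio, with logistic standardisation, was 1.17, a cut of 1 - 1/1.17 = 14.5%.

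**Same case with b = 0.7.** T = sqrt(12.96 + 125.44) = 11.76, rates 0.422 and 0.097, standard error 0.112, 1-SD shift 0.023. Removable share = (0.023/0.112)^2 = 4.2%. The simulated ratio was 1.05 with logistic standardisation and 1.02 with a linear model.

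**Ranges for SDAI <=11 at Week 8**

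| Quantity | Slope 0.2-0.6 | Slope 0.7-0.8 |
|---|---|---|
| Variance cut from adjustment | about 1-20% | close to nil; a linear model can lose up to about 2% |
| Shift per 1-SD imbalance | about 2-6 points | smaller |
| Crude standard error | about 11-13 points | similar or slightly lower |

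**How often it matters.** At s = 12, an imbalance of 5 points or more has probability 2 x [1 - Phi(5/3.46)] = about 15%. With no treatment effect, the crude test rejected in 5-7% of all simulated trials and in 6-13% of those imbalanced trials.

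**Remission (SDAI <=3.3).** At m = 40, the chance of no placebo remission at all is about 20-60%. For example, with a 2.6% placebo rate it is 0.974^20 = 59%. An adjusted model is unstable there, and the gain is small or nil at steeper slopes.

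**The case against.** The strongest reply is that nothing here is invalid. Under randomisation the crude difference is unbiased, and its standard error already includes the variation from chance imbalance. A reader might infer that the responder results are biased, or that imbalance makes them wrong. The documents do not support that: allocation is randomised, and the argument concerns efficiency and one's reading conditional on the imbalance observed. This part of the reply stands.

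Size also counts against the point. A 1-SD imbalance moves the estimate by at most about half a standard error. In the worked case, a 95% half-width of 1.96 x 12.3 = 24 points becomes 24 x sqrt(1/1.17) = 22. The gain rests on assumed baseline values and fades as the slope steepens. This stands too.

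A reader might also infer that all 30 comparisons lose useful precision. That has not been shown. Only SDAI at Week 8 was simulated; the DAS28 comparisons (24 of 30) and Weeks 4 and 6 were not, and remission gains little.

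Finally, these are secondary endpoints in a Phase 2a trial. The only decision rule (SAP 5.1) uses the baseline-adjusted primary model, and SDAI and DAS28 change have baseline-adjusted MMRM analyses. That lowers the stakes, but it does not supply an adjusted responder difference.

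**Conclusion.** The point holds as a modest efficiency and robustness gap. The SAP treats baseline as prognostic in its change models and leaves it out of the endpoints whose definition depends on it. For SDAI <=11 at Week 8, adjustment would cut the variance by about 1-20% and remove a shift of about 2-6 percentage points per 1-SD imbalance, against a standard error of about 11-13. This assumes baseline mean 38-42, SD 10-14 and slope 0.2-0.6; at steeper slopes little is gained. The reasoning should carry over to DAS28 low disease activity, but its size there is unknown. The results do not support replacing the crude difference, nor relying on adjustment for remission. The choice of interval method for small counts is a separate matter.

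**What to change.** In SAP 5.2.1, 6.2.1, 6.2.2 and Appendix 1, before unblinding:
- For low disease activity (SDAI and each DAS28 version, Weeks 4, 6 and 8), add one baseline-adjusted risk difference. Fit a logistic regression of response on treatment and the baseline score of the same index, optionally with the anti-TNF stratum, and standardise it to a risk difference. Name the variance method. Use this one model only; the linear alternative can lose precision at steep slopes.
- Report it beside the crude rates and crude difference, for both observed and NRI data.
- Fix a minimum responder count per arm below which only the crude result is given, so that the choice does not depend on the results.
- Keep remission crude, with any adjusted result supportive at most.

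SAP Section 1 says that study baseline SDAI data had been reviewed by version 2, so the sponsor can replace the assumed mean and SD with pooled values and check the expected gain.

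The cost is SAP wording and one extra model per table, with no new data. The adjusted difference will not equal the subtraction of the two crude percentages, which needs a footnote.
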